3.2.2.6 Time to death or distant metastasis (TTDM)

TTDM (per RECIST 1.1 as assessed by BICR) will be defined as the time from the date of randomisation until the first date of distant metastasis or death in the absence of distant metastasis. Distant metastasis is defined as any new lesion that is outside of the radiation field according to RECIST 1.1. For this reason, the TTDM endpoint will be determined from recurrent disease that occurs outside of the structures contained within the thorax, including lymph nodes, pulmonary, pleural, and mediastinal metastatic sites and excluding the heart. The locations of distant metastases will be defined and documented prior to database lock/unblinding.

Patients who have not developed distant metastasis or died at the time of analysis will be censored at the time of the latest date of assessment from their last evaluable RECIST 1.1 assessment. However, if the patient has distant metastasis or dies after 2 or more missed visits, the patient will be censored at the time of the latest RECIST 1.1 assessment prior to the 2 missed visits. If the patient has no evaluable visits or does not have baseline data, they will be

censored at Day 1 unless they die within 2 visits of baseline, which then will be treated as an event with date of death as the event date.

3.2.2.7 **Time from randomisation to second progression or death (PFS2)**

Time from randomisation to second progression or death (PFS2) will be defined as the time from the date of randomisation to the earliest of the progression event subsequent to first subsequent therapy, or death.

There are two preconditions to have PFS2 second progression event: 1) observation of primary PFS event (first progression) by Investigator; 2) received subsequent anti-cancer therapy. The primary PFS event includes only radiological progression by RECIST 1.1, as per Investigator.

The date of second progression will be recorded by the Investigator in the eCRF and defined according to local standard clinical practice and may involve any of the following: objective radiological imaging, symptomatic progression, or death. Second progression status will be reviewed ($q8w \pm 1$ week for the first 48 weeks [relative to the date of randomisation] and then $q12w \pm 1$ week [the first progression]) following the first progression event used for the primary variable PFS and status recorded.

Subsequent anti-cancer therapy considered in PFS2 assessment include systemic treatment (chemotherapy, targeted therapy, immunotherapy, etc.) and definitive radiotherapy. Palliative radiotherapy and other local treatment such as surgery are not considered as subsequent anti-cancer therapy in PFS2 assessment.

If death occurs without first or second progression, the death will be a PFS2 death event irrespective of whether subsequent therapy has started.

Patients alive and for whom a second disease progression has not been observed should be censored at date last known alive and without a second disease progression (i.e. censored at:

- The PFS assessment date if the patient has not had a first progression or death (PFS censoring date)
- The date the patient is last known to not have received a first subsequent therapy (latest TTSCAPRX=No) or the date known to be alive for any patient without a TTSCAPRX form if a patient has had a first progression and not started a subsequent therapy (TFST censoring date)
- The latest PFS2 assessment date if the patient has started a first subsequent therapy and PFS2 event (second progression or death) has not been observed).

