- ^f Following the first progression event used for the primary variable, PFS (the first progression), the site will be asked on a regular basis (q8w ±1 week for the first 48 weeks [relative to the date of randomisation], and then q12w ±1 week) if the participant has had a second progression event. Actual timing of assessments for a second progression event will be according to local standard practice. PFS2 assessment will be performed by the Investigator and defined according to local standard clinical practice and may involve any of the following: objective radiological imaging, symptomatic progression, or death. (The follow-up scan confirming an immediate RECIST 1.1-defined radiological progression is not to be considered as the second progression.)
- ^g For participants who discontinue their assigned IP following progression, available readings of CT/MRI from local practice will be collected from participants` medical charts whilst information on subsequent anticancer treatment and/or PFS2 is collected.
- ^h Participants may be contacted in the week following DCOs to confirm survival status. Details of any treatment for NSCLC (including surgery) post the last dose of IP must be recorded in the eCRF. Participants who decline to return to the study site for evaluations should be contacted by telephone as indicated in the SoAs as an alternative.
- ⁱ Free T3 or free T4 will only be measured if TSH is abnormal or if there is clinical suspicion of an AE related to the endocrine system.
- ^j See Section 6.1.3 and Section 8.1 for additional details relevant to tumour assessment.

ADA Anti-drug antibody; AE Adverse event; C Cycle; CT Computed tomography; DCO Data cutoff; ECOG Eastern Cooperative Oncology Group; eCRF Electronic case report form; EORTC QLQ-C30 European Organisation for Research and Treatment of Cancer 30-item core quality of life questionnaire; EQ-5D-5L EuroQoL 5-dimension, 5-level health state utility index; IP Investigational Product; MRI Magnetic resonance imaging; NSCLC Non-small cell

AstraZeneca

lung cancer; PD Progression of disease; PFS2 Time from randomisation to second progression; PK Pharmacokinetic; q8w Every 8 weeks; q12w Every 12 weeks; QLQ-LC13 13-item self-administered questionnaire for lung cancer; SAE Severe Adverse Event; RECIST Response Evaluation Criteria in Solid Tumors; T₃ Triiodothyronine; T₄ Thyroxine; TSH Thyroid-stimulating hormone; WHO World Health Organization

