During the Treatment Period, participants who are clinically stable at an initial Response Evaluation Criteria in Solid Tumors 1.1-defined radiological progression of disease may continue to receive study treatment at the discretion of the Investigator and participants. A follow-up scan is to be collected after the initial Response Evaluation Criteria in Solid Tumors 1.1-defined radiological progression of disease, no less than 4 weeks after the prior assessment of progression of disease and no later than the next regularly scheduled imaging visit, and this scan is evaluated using the Confirmation of Radiological Progression criteria outlined in Appendix E. Participants with confirmed PD who continue to receive study treatment at the discretion of the Investigator and participant (following consultation with AstraZeneca) can receive treatment until no longer having clinical benefit, and tumor
assessments should continue on their regular imaging schedule for the duration of treatment. If the subsequent scan does not confirm the immediate prior radiological progressive disease, scanning should continue until the next Response Evaluation Criteria in Solid Tumors 1.1defined radiological progression of disease, which in turn will require a subsequent scan evaluated using the Confirmation of Radiological Progression criteria outlined in Appendix E.

Follow-up of participants post discontinuation of study treatment

Participants who have discontinued study treatment due to toxicity or symptomatic deterioration, clinical progression, or who have commenced subsequent anticancer therapy will be followed up with tumour assessments until Response Evaluation Criteria in Solid Tumors 1.1-defined radiological progression of disease plus an additional follow-up scan or until death (whichever comes first) and followed for survival. PRO questionnaires will be followed up until PFS2.

Survival

All participants randomised in the study should be followed up for survival.

Independent Data Monitoring Committee:

The Independent Data Monitoring Committee will meet periodically in accordance with the IDMC charter to review safety assessments and make recommendations to continue, amend, or stop the study based on safety findings.

Full details of the Independent Data Monitoring Committee procedures and processes can be found in the Independent Data Monitoring Committee Charter.

Statistical methods

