9.4.1.8 Time from randomisation to second progression

Time from randomisation to second progression or death (PFS2) will be defined as the time from the date of randomisation to the earliest of the progression event subsequent to first subsequent therapy, or death. The date of second progression will be recorded by the Investigator in the eCRF and defined according to local standard clinical practice and may involve any of the following: objective radiological imaging, symptomatic progression, or death. Second progression status will be reviewed (q8w ± 1 week for the first 48 weeks [relative to the date of randomisation], and then q12w ± 1 week (the first progression)) and status will be recorded. Censoring details for this endpoint will be defined in the SAP.

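### SAP 3.2.2.7 counts a second progression towards PFS2 only after an Investigator RECIST progression, a condition that the protocol's PFS2 definition does not contain

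*SAP*

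**What the plan says.** **Definition.** Protocol 9.4.1.8 measures PFS2 from randomisation to "the earliest of the progression event subsequent to first subsequent therapy, or death". It lets the Investigator establish second progression by imaging, by symptoms or by death, and leaves censoring details to the SAP. SAP 3.2.2.7 opens with the same definition.

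**Added rule.** SAP 3.2.2.7 then lists "two preconditions to have PFS2 second progression event: 1) observation of primary PFS event (first progression) by Investigator"; the second precondition is receipt of subsequent therapy. It goes on: "The primary PFS event includes only radiological progression by RECIST 1.1, as per Investigator".

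**Death.** The same section makes death without a first or second progression a PFS2 event, whether or not next-line therapy has begun.

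**Censoring.** There are three bullets. The first uses "The PFS assessment date if the patient has not had a first progression or death (PFS censoring date". The second covers a patient with a first progression and no subsequent therapy. The third uses the latest PFS2 assessment for a patient who has started subsequent therapy and has no PFS2 event.

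**Who is affected.** Protocol 7.1 lists clinical progression among the reasons to stop study treatment. The Synopsis expects patients who have "discontinued study treatment due to toxicity or symptomatic deterioration, clinical progression, or who have commenced subsequent anticancer therapy", and follows them with scans. Protocol 7.1.1 continues the scans whether or not new therapy has started.

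**Data collection.** Protocol Table 2 footnote f, repeated in 8.1.3, reads: "Following the first progression event used for the primary variable, PFS (the first progression), the site will be asked on a regular basis".

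**Declaration.** SAP section 6 lists two changes from the protocol, one on time to deterioration and one on TTDM. The PFS2 precondition is not among them.

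**The concern.** The definition and the precondition can give different results for the same patient. A condition for having an event is more than a censoring detail, so the protocol's deferral to the SAP does not cover it. The patients concerned are foreseen: they stop for clinical progression, start next-line therapy without a RECIST PD, and progress on that therapy.

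PFS2 is a secondary endpoint, analysed by stratified log-rank test with an HR and p-value (SAP 4.2.2.7). Its purpose is to show whether benefit carries through the next line. If a recorded failure on that line is set aside because no RECIST PD came first, the endpoint omits what it was meant to capture, and censoring a patient with a known progression is informative. Two programmers working from this text could also derive different dates.

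**Working it through.** The documents give no PFS2 event count, power or HR, so there is no stated figure to reproduce. The check has two parts: trace the rules on a worked patient, then see how much they could matter.

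**Worked patient (dates assumed).** No RECIST PD at the week 16 scan (day 16 × 7 + 1 = 113). Next-line therapy starts on day 140 for clinical progression. Scheduled scans at week 24 (24 × 7 + 1 = day 169) and week 32 (32 × 7 + 1 = day 225) also show no RECIST PD.

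| Later course | Protocol 9.4.1.8 | SAP 3.2.2.7 |
|---|---|---|
| (a) Symptomatic progression day 260, alive | Event day 260 | No event. Bullet 1: censored day 225, the last evaluable scan. Bullet 3: censored at the latest PFS2 assessment |
| (b) RECIST PD day 260, further progression day 380 | Event day 260 | Day 260 or day 380, depending on the order required |
| (c) Symptomatic progression day 260, death day 400 | Event day 260 | Death event day 400 |

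- In (a) both bullets fit: the patient has had no qualifying first progression and has started subsequent therapy. No priority is stated. Had scanning stopped after day 113, bullet 1 would give day 113. Because the site prompt follows the first PFS progression, there may be no PFS2 assessment on file for bullet 3.
- In (b) the SAP does not say that the RECIST PD must precede the new therapy. Read literally, day 260 meets both preconditions. Read by the words first and second, day 260 is the first progression and the event falls 380 − 260 = 120 days later.
- In (c) the event moves by 400 − 260 = 140 days.

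Courses (a) and (c) conflict with the definition on either reading.

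**Exposure.** The rate of starting next-line therapy before an Investigator RECIST PD is assumed to be 5–15%. With 375 mITT patients (SAP 1.3): 375 × 0.05 = 18.75, about 19; 375 × 0.15 = 56.25, about 56. Only those who progress on next-line therapy before the DCO are affected.

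**Effect on the HR (illustration; every rate assumed).** 375 patients, 2:1, 200 replicates, with both derivations applied to the same simulated patients. Exponential times: placebo median to first progression 9 months with HR 0.65; then median 7 months to progression on next-line therapy, half of these RECIST PD; from there, median 5 months to a further progression and 8 months to death. DCO at 24–48 months. Both ambiguities were resolved unfavourably: RECIST PD on next-line therapy was taken as the first progression, and bullet 1 censored at about the time of clinical progression.

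| Clinical-progression rate, durvalumab / placebo | Events, protocol | Events, SAP | Lost | Moved later | HR, protocol | HR, SAP |
|---|---|---|---|---|---|---|
| 5% / 5% | 270 | 267 | 2.7 | 10.7 | 0.692 | 0.691 |
| 10% / 10% | 270 | 265 | 5.3 | 21.7 | 0.692 | 0.691 |
| 20% / 20% | 270 | 260 | 10.4 | 43.0 | 0.692 | 0.688 |
| 5% / 15% | 270 | 266 | 4.4 | 19.2 | 0.692 | 0.711 |
| 15% / 5% | 270 | 264 | 6.2 | 23.9 | 0.692 | 0.671 |

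At 5% in both arms, 2.7 + 10.7 = 13.4 patients are affected out of about 19 exposed. At 20%, it is 10.4 + 43.0 = 53.4 out of 375 × 0.20 = 75. With unequal rates the HR moves by 0.711 − 0.692 = +0.019 or 0.671 − 0.692 = −0.021.

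**The case against.** The best defence is that the endpoint is called second progression, and the protocol itself (Table 2 footnote f and 8.1.3) has second progression follow the first PFS progression. On that view the SAP settles a tension already in the protocol, and its amendment history does record that PFS2 preconditions were added in version 2.0. Without the precondition, a patient who switches therapy after toxicity and then progresses for the first time has a PFS2 event at that first progression. TFST and TSST are planned and do not depend on RECIST PD. PFS2 is outside the testing hierarchy in protocol 9.1.

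Much of this stands. The tension does begin in the protocol, alpha is untouched, and a declared precondition would be a defensible choice. But the two definition sentences are explicit and do not contain the condition, section 6 is silent, and the censoring bullets overlap whichever choice is made. TFST and TSST time the start of treatments, so they do not replace a progression date.

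A reader might also infer more than the text supports:

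- That no PFS2 event is possible without a RECIST PD. Death counts regardless.
- That a RECIST PD on next-line therapy is certainly relabelled as the first progression. The SAP states no order.
- That case (a) is certainly censored at the PFS date. The third bullet fits equally well.
- That BICR governs the precondition. The SAP names the Investigator; the BICR difficulty lies only in the protocol's prompt.

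**Conclusion.** The point holds for the second-progression component of PFS2. SAP 3.2.2.7 adds an undeclared condition that conflicts with the protocol definition and with the SAP's own first sentence. For patients who start next-line therapy after clinical progression without RECIST PD, a symptomatic progression on that therapy is lost to censoring or deferred to death. A RECIST PD has two possible dates, and the censoring date is not determined.

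The size is uncertain. The figure of 19–56 is exposure under an assumed 5–15%, and it would be wrong to read it as that many lost or delayed events. Nor do the documents support a claim that the rule favours durvalumab: they give neither the rate nor any imbalance between arms. In the illustration the HR barely changes at equal rates and shifts by about 0.02, in either direction, when rates differ by 10 percentage points. The primary and key secondary conclusions are unaffected. It is worth correcting because a named secondary endpoint should have one event date per patient, and that date should match its definition.

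**What to change.** **SAP 3.2.2.7, event.** Remove the RECIST-PD precondition. The PFS2 event is then the first Investigator-recorded progression, radiological or symptomatic, after the start of first subsequent therapy, or death. If the sponsor prefers to keep the precondition, declare it in section 6, state the required order of RECIST PD and subsequent therapy, and add a sensitivity analysis under the protocol definition.

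**SAP 3.2.2.7, censoring (either way).** Apply the first bullet only to patients with neither a first progression nor subsequent therapy. Apply the latest-PFS2-assessment bullet to anyone who has started subsequent therapy.

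**Protocol Table 2 footnote f and 8.1.3.** Start the site's second-progression prompt at the earlier of Investigator progression and start of subsequent therapy. At present it refers to the event used for the primary variable, which is BICR-based, and protocol 8.1.1 keeps BICR results from Investigators.

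**Cost.** SAP wording, programming and a clarification of the eCRF prompt; no added visits or scans. The downside is that a first-ever progression after a switch without prior PD becomes the PFS2 event, as the protocol definition already implies.

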3.2.3 Patient-reported outcomes (PRO)

Symptoms and overall quality of life (QoL) will be assessed using the PRO questionnaires, European Organisation for Research and Treatment of Cancer (EORTC) 30-item core (QoL) questionnaire (QLQ-C30) ([Aaronson et al 1993](#)) and 13-item lung cancer QoL questionnaire (QLQ-LC13) ([Bergman et al 1994](#)) (secondary endpoints). All questionnaires will be scored according to published guidelines or the developer's guidelines, if published guidelines are not available. All PRO data will be collected until PFS2.

3.2.3.1 EORTC QLQ-C30 and QLQ-LC13

The EORTC QLQ-C30 consists of 30 questions that can be combined to produce 5 functional scales (physical, role, cognitive, emotional, and social), 3 symptom scales (fatigue, pain, and nausea/vomiting), 6 individual items (dyspnoea, insomnia, appetite loss, constipation, diarrhoea and perceived financial impact of disease), and a global measure of health status. The global health status/QoL will be assessed using 2 items from the QLQ-C30: "How would you rate your overall health during the past week? (Item 29) and "How would you rate your overall QoL during the past week? (Item 30).

The QLQ-LC13 is a lung cancer specific module from the EORTC for lung cancer comprising 13 questions to assess lung cancer symptoms (cough, haemoptysis, dyspnoea, and site-specific pain), treatment-related symptoms (sore mouth, dysphagia, peripheral neuropathy, and alopecia), and pain medication. Except for a multi-item scale for dyspnoea, all are single items. The dyspnoea scale will only be used if all 3 items have been scored; otherwise, the items are treated as single-item measures.

An outcome variable consisting of a score from 0 to 100 will be derived for each of the symptom scales/symptom items, the functional scales and the global health status/QoL scale in the QLQ-C30 according to the EORTC QLQ-C30 Scoring Manual ([EORTC QLQ-C30 Scoring Manual, Third Edition](#)) and for each of the symptom scales/items in the QLQ-LC13 according to the EORTC QLQ-LC13 instructions.

Higher scores on the global health status/QoL and functioning scales indicate better health status/function, but higher scores on symptom scales/items represent greater symptom severity. For each scale, if <50% of the scale items are missing, then the scale score will be divided by the number of non-missing items and multiplied by the total number of items on the scales ([Fayers et al 2001](#)). If at least 50% of the items are missing, then that scale will be treated as missing. Missing single items are treated as missing. The reason for any missing questionnaire will be identified and recorded. If there is evidence that the missing data are systematic, missing values will be handled to ensure that any possible bias is minimised.

The five symptoms that have been identified as primary PRO endpoints are:

- Dyspnoea: multi-item scale based on 3 questions (“Were you short of breath when you rested; walked; climbed stairs?” – QLQ-LC13)
- Cough: 1 item (“How much did you cough?” – QLQ-LC13)
- Chest pain: 1 item (“Have you had pain in your chest?” – QLQ-LC13)
- Fatigue: multi-item based on 3 questions (“Did you need rest?; Have you felt weak?; Were you tired?” – QLQ-C30)
- Appetite loss: 1 item (“Have you lacked appetite?” – QLQ-C30)

The physical functioning and overall health status domains of the EORTC QLQ-C30 are furthermore pre-specified endpoints of interest.

Change from baseline

Change from baseline in the key PRO symptom scores of dyspnoea (LC13), cough (LC13), pain in chest (LC13), fatigue (C30) and appetite loss (C30), physical functioning (C30) and overall health status (C30) will be analysed making use of all data from baseline.

Definition of clinically meaningful changes

A minimum clinically meaningful change is defined as an absolute change in the score from baseline of ≥ 10 for scales/items from the EORTC QLQ-C30 and the QLQ-LC13 (Osoba et al 1998). For example, a clinically meaningful improvement in physical function (as assessed by EORTC QLQ-C30) is defined as an increase in the score from baseline ≥ 10 , whereas a clinically meaningful deterioration is defined as a decrease in the score from baseline of ≥ 10 . At each post-baseline assessment, the change in symptoms/functioning from baseline will be categorised as improvement, no change, or deterioration, as shown in Table 7.

Table 7 Visit response in symptoms, functioning, and global health status/QoL

Score	Change from baseline	Visit response
EORTC QLQ-C30 /QLQ-LC13 symptom scales/items	$\geq + 10$	Worsened
	$\leq - 10$	Improved
	Otherwise	Stable
EORTC QLQ-C30 functional scales and global health status/QoL	$\geq + 10$	Improved
	$\leq - 10$	Worsened
	Otherwise	Stable

Time to symptom deterioration/worsening (QLQ-C30 and QLQ-LC13)

For each of the symptoms scales/items in the EORTC QLQ-C30 and QLQ-LC13, time to symptom deterioration/worsening will be defined as the time from randomisation until the date of the first clinically meaningful symptom deterioration/worsening (an increase in the score from baseline of ≥ 10) that is confirmed at the next available subsequent assessment at least 14 days apart, or death (by any cause) in the absence of a clinically meaningful symptom deterioration/worsening, regardless of whether the patient withdraws from IP or receives another anti-cancer therapy prior to symptom deterioration/worsening. Missed visits are allowed in between assessments confirming deterioration/worsening. This is considered a conservative approach whereby a deterioration/worsening is considered a 'negative' outcome and therefore should be assigned as such, regardless of missed visits. Death will be included as an event only if the death occurs within 2 visits of the last PRO assessment where the symptom change could be evaluated. Patients with a single deterioration/worsening and no further assessments will be treated as deteriorated in the analysis.

Patients whose symptoms (as measured by EORTC QLQ-C30 and QLQ-LC13) have not shown a clinically meaningful deterioration/worsening and who are alive at the time of the analysis will be censored at the time of their last PRO assessment where the symptom could be evaluated. Also, if symptoms deteriorate after 2 or more missed PRO assessment visits or the patient dies after 2 or more missed PRO assessment visits, the patient will be censored at the time of the last PRO assessment where the symptom could be evaluated, prior to the 2 missed assessment visits. The 2 missed visit rule for ePRO will take a 'look-forward' approach i.e. if there are 2 consecutive missed visits at any time prior to the confirmed deterioration event, the event will be censored at the last available assessment prior to the 2 missed visits. Confirmation of deterioration will be first determined, then the censoring rules will be applied.

See Appendix A for further details on the derivation of the confirmation of deterioration 2 missed visit rule for ePRO and length of 2 missed visit window.

If the patient has no evaluable visits or does not have baseline data, they will be censored at day 1 unless they die within 2 visits of baseline (8 weeks plus 3 days allowing for a late assessment within the visit window).

The population for the analysis of time to symptom deterioration will include patients who have baseline scores of ≤ 90 .

Time to HRQoL/function deterioration/worsening (QLQ-C30)

For HRQoL and function (as measured by EORTC QLQ-C30), time to deterioration/worsening will be defined as the time from the date of randomisation until the date of the first clinically meaningful deterioration/worsening (a decrease in the function scales or the global health status/QoL score from baseline of ≥ 10) that is confirmed at the next available subsequent assessment at least 14 days apart, or death (by any cause) in the absence of a clinically meaningful deterioration/worsening, regardless of whether the patient withdraws from IP or receives another anti-cancer therapy prior to HRQoL/function deterioration/worsening. Missed visits are allowed in between assessments confirming deterioration. This is considered a conservative approach whereby a deterioration is considered a 'negative' outcome and therefore should be assigned as such, regardless of missed visits. Death will be included as an event only if the death occurs within 2 visits of the last PRO assessment where the HRQoL/function change could be evaluated. Patients with a single deterioration/worsening and no further assessments will be treated as deteriorated in the analysis.

Patients whose HRQoL or function have not shown a clinically meaningful deterioration/worsening and who are alive at the time of the analysis will be censored at the time of their last PRO assessment where the HRQoL/function could be evaluated, prior to the 2 missed visits. Also, if HRQoL or function deteriorates after 2 or more missed PRO assessment visits or the patient dies after 2 or more missed PRO assessment visits, the patient will be censored at the time of the last PRO assessment where HRQoL/function could be evaluated. The 2 missed visit rule for ePRO will take a 'look-forward' approach i.e. if there are 2 consecutive missed visits at any time prior to the confirmed deterioration event, the event will be censored at the last available assessment prior to the 2 missed visits. Confirmation of deterioration will first be determined, then the censoring rules will be applied. If the patient has no visits or does not have baseline data, they will be censored at day 1 unless they die within 2 visits of baseline (8 weeks plus 3 days allowing for a late assessment within the visit window).

See Appendix A for further details on the derivation of the confirmation of deterioration, 2-missed visit rule and length of 2 missed visit window.

The population for the analysis of time to QoL/function deterioration/worsening will include patients who have baseline scores of ≥ 10 .

Symptom improvement rate (QLQ-C30 and QLQ-LC13)

The symptom improvement rate will be defined as the number (%) of patients with a minimum of 2 consecutive assessments at least 14 days apart that show a clinically meaningful improvement (a decrease in score of ≥ 10) in that symptom from baseline. Missed visits are not allowed in between consecutive assessments of improvement. This is considered a conservative approach whereby an improvement is considered a 'positive' outcome and therefore for any avoidance of doubt in the assessment of an improvement, missed visits are not allowed.

The denominator will consist of the subset patients who have a baseline symptom score of ≥ 10 .

HRQoL/function improvement rate (QLQ-C30)

The HRQoL/function improvement rate will be defined as the number (%) of patients with a minimum of 2 consecutive assessments at least 14 days apart that show a clinically meaningful improvement (an increase in score of ≥ 10) in that scale from baseline. Missed visits are not allowed in between consecutive assessments of improvement. This is considered a conservative approach whereby an improvement is considered a 'positive' outcome and therefore for any avoidance of doubt in the assessment of an improvement, missed visits are not allowed.

The denominator will consist of the subset of patients who have a baseline QoL/function score of ≤ 90 .

